#### INTERVENTION AND DURATION

Participants will receive guselkumab 100 mg SC injections at Weeks 0, 4, 12, 20 and 28.

The first dose of the guselkumab will always be administered at the site and by a health care professional (HCP). Subsequent doses can be self-administered at the site under supervision by site-staff after the participant has been adequately trained in the procedure.

The total duration of the study will be 40 weeks, including 28 weeks of treatment and a Final Efficacy Visit 4 weeks later (Week 32). A Final Safety Visit will occur 12 weeks after the last dose of the guselkumab (Week 40). For participants continuing to receive guselkumab commercially after the end of the study, the Final Safety Visit will occur on the same day as the first dose of guselkumab outside the study, ie, at Week 36.

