#### SAFETY EVALUATIONS

The safety and tolerability of guselkumab will be monitored by collecting information on adverse events, clinical laboratory tests, physical examinations, vital signs, and concomitant medication review through Week 40.

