## 3. OBJECTIVES AND ENDPOINTS

Objectives	Endpoints			
Primary				
To evaluate the effect of guselkumab on CFR measured by transthoracic doppler-echocardiography, in participants with moderate-to-severe psoriasis and intermediate cardiovascular risk*.	• Change from baseline † in CFR at Week 32.			
Secondary				
To evaluate the short-term effect of guselkumab on CFR measured by transthoracic doppler-echocardiography, in participants with moderate-to-severe psoriasis and intermediate cardiovascular risk.	Change from baseline in CFR at Week 16.			
To evaluate the effect of guselkumab on GLS as a surrogate marker of left ventricular function in participants with moderate-to-severe psoriasis and intermediate cardiovascular risk.	
 
Change from baseline in GLS at Week 32.
 
Change from baseline in GLS at Week 16.
 
			
To evaluate the effect of guselkumab on arterial stiffness in participants with moderate-to-severe psoriasis and intermediate cardiovascular risk.	
 
Change from baseline in cfPWV at Week 32.
 
Change from baseline in cfPWV at Week 16.
 
			
To evaluate the effect of guselkumab on CFR among participants in the different CFR categories.	
 
Change from baseline in CFR at Week 16 and Week 32 among participants with CFR in the ranges of 2 to 2.49, 2.5 to 3, and 3.01 to 3.5 at baseline.
 
			
To evaluate the effect of guselkumab on surrogate CV risk markers among nicotine users and non-users in the participant population.	
 
Change from baseline in CFR at Week 16 and Week 32 among nicotine users and non-users.
 
Change from baseline in GLS at Week 16 and Week 32 among nicotine users and non-users.
 
Change from baseline in cfPWV at Week 16 and Week 32 in nicotine users and non-users.
 
			
To assess the safety and tolerability of guselkumab in participants with moderate-to-severe plaque psoriasis and intermediate cardiovascular risk.	Rate of AEs among participants treated with guselkumab.			

\* Intermediate cardiovascular risk defined by CFR ≥2 and ≤3.5 at Screening Visit S2.

**Abbreviations:** AE= Adverse event; cfPWV = carotid-femoral pulse wave velocity; CFR= Coronary Flow Reserve; GLS: Global Longitudinal Strain

The G-CARE study will also investigate the following exploratory objectives:

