5.4. Secondary Endpoint(s) Analysis

5.4.1. Key Confirmatory Secondary Endpoint(s)

The key secondary endpoints include the following at Week 16 and Week 32:

- Change from baseline in CFR at Week 16
- Change from baseline in absolute GLS at Week 16 and Week 32.
- Change from baseline in carotid-femoral pulse wave velocity (cfPWV) at Week 16.
- Change from baseline in cfPWV at Week 32.
- Change from baseline in CFR at Week 16 and Week 32 among participants with CFR in the ranges of 2 to >2.75 and ≤ 2.75 to 3.5 at baseline.
- Change from baseline in CFR at Week 16 and Week 32 among nicotine users and non-users.
- Change from baseline in absolute GLS at Week 16 and Week 32 among nicotine users and non-users.
- Change from baseline in cfPWV at Week 16 and Week 32 in nicotine users and nonusers.
- Rate of Adverse Events (AEs) among participants treated with guselkumab at Week 16 and Week 32.

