5.6.2. Adverse Events

The verbatim terms used in the case report form (CRF) by investigators to identify adverse events (AEs) will be coded using the latest version of Medical Dictionary for Regulatory Activities (MedDRA) (System Organ Class and Preferred Term).

Any AE occurring at or after administration of adenosine or the initial administration of study intervention (guselkumab) through the day of last dose within the study phase plus 12 weeks or the date of the Final Safety visit, whichever is the latest, is considered to be treatment emergent adverse event (TEAE). If the event occurs on the day of the initial administration of study intervention, and either event time or time of administration are missing, then the event will be assumed to be TEAE. If the event date is recorded as partial or completely missing, then the event

will be considered to be TEAE unless it is known to be prior to the first administration of study intervention based on partial onset date or resolution date. All reported TEAEs will be included in the analysis.

For each adverse event, the number and percentage of participants who experience at least 1 occurrence of the given event will be summarized by Nicotine use, non-Nicotine use and Total group.

Any usual pharmacodynamic actions and expected effects of adenosine administration (refer to Appendix 6.11) of CFR assessment are not considered as AEs

Summary tables will be provided for TEAEs.

The incidence of other TEAEs of special interest will be summarized. See Appendix 8 for list of adverse events in each category.

Listing of all serious adverse events (SAEs) will be provided along with abnormalities of laboratory, vital signs, and other physical observations.

Deaths will be displayed by actual intervention received. Frequencies for the following parameters will be included in the summary table:

- Number of participants who died
- Cause of death
- Relationship to study intervention (yes/no)

A listing of participants who died will be provided.

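### SAP 5.4.1 ties the adverse-event rate endpoint to Week 16 and Week 32, in conflict with the protocol endpoint and with the SAP's own TEAE window

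*SAP*

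**What the plan says.** Protocol Section 3 gives one safety endpoint, "Rate of AEs among participants treated with guselkumab", with no time point. The protocol synopsis says safety is monitored by adverse events, laboratory tests, "physical examinations, vital signs, and concomitant medication review through Week 40". The Final Safety Visit is 12 weeks after the last dose, which is Week 40 for a full course. For participants who move to commercial guselkumab it is the visit of the first outside dose, planned at Week 36.

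SAP 5.4.1 opens its list with "The key secondary endpoints include the following at Week 16 and Week 32". The adverse-event bullet repeats the timing in its own text: "Rate of Adverse Events (AEs) among participants treated with guselkumab at Week 16 and Week 32".

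SAP 5.6.2 works on a different time frame. TEAEs run from the first adenosine or guselkumab administration "through the day of last dose within the study phase plus 12 weeks or the date of the Final Safety visit", whichever is later. It adds that "All reported TEAEs will be included in the analysis". The statistic is the number and percentage of participants with at least one occurrence, with no visit cut.

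SAP 5.4.1.1 to 5.4.1.3 define and model only CFR, GLS and cfPWV. Appendix 2, which records departures from the protocol, covers visit timing, analysis sets and CFR ranges. It does not mention time points for the adverse-event endpoint.

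**The concern.** Week 16 and Week 32 are the imaging visits. They suit CFR, GLS and cfPWV, which are measured at those visits. Adverse events accrue continuously, so a visit label on an event rate needs a rule: cumulative to the visit, within the visit window, or something else. The SAP gives none. The most natural literal reading, cumulative to the visit, closes the endpoint while follow-up for adverse events is still open.

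The stake is that the clinical study report could carry two different figures for one quantity: a Week 32 rate labelled as the protocol's secondary endpoint, and a full-window TEAE percentage in the safety tables. A shorter window can only lower the percentage with at least one event or leave it unchanged. Because Appendix 2 is silent, a reader could not tell whether the narrower figure was intended.

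**Working it through.** **Inputs.** SAP Table 2 gives target days 197 (Week 28), 225 (Week 32) and 281 (Week 40), and a Final Efficacy Visit interval of days 211 to 252 (longer for CFR only). Footnote c puts the Final Efficacy Visit 4 to 8 weeks after the last dose following premature termination. SAP 5.6.2 ends the TEAE window at last dose plus 12 weeks (84 days) or the Final Safety Visit, whichever is later, so 12 weeks is a minimum.

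**Reproducing the SAP's end date.** Study day = 7 × week + 1. Week 28: 7 × 28 + 1 = 197. Adding 84 gives 281, which equals 7 × 40 + 1 and matches Table 2.

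**Full course, 12-week follow-up.** Gap = 281 − 225 = 56 days; 56/281 = 19.9%. If the cut falls at the edges of the Table 2 interval, the gap is 281 − 211 = 70 days (24.9%) or 281 − 252 = 29 days (10.3%).

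**Full course, switch to commercial guselkumab at Week 36.** Week 36 is day 253. Protocol 8.3.1 ends general adverse-event reporting at the last study-related procedure, so the observed gap is about 253 − 225 = 28 days.

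**Stopped by the termination.** With the Final Efficacy Visit g weeks after the last dose, gap = 84 − 7g days.
- g = 4: 84 − 28 = 56 days (8 weeks).
- g = 8: 84 − 56 = 28 days (4 weeks).

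If such a participant starts commercial drug 8 weeks after the last study dose (an assumption), the observed gap falls to 8 − g, that is 0 to 4 weeks.

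These termination figures assume that Week 32 in the bullet means the Final Efficacy Visit, as Appendix 2 says for the efficacy endpoints. If it means calendar day 225, a participant whose last dose was at Week 20 has a 12-week window ending at 141 + 84 = 225, so nothing is cut; the same holds for any earlier last dose. The SAP does not say which meaning applies to adverse events.

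**Effect on the percentage with at least one event (illustration).** The documents give no adverse-event rate. Assume a constant hazard and let p be the percentage by day 281. The percentage by day 225 is then 1 − (1 − p)^(225/281).

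| Assumed p by day 281 | By day 225 | Difference |
|---|---|---|
| 30% | 24.8% | 5.2 points |
| 50% | 42.6% | 7.4 points |
| 70% | 61.9% | 8.1 points |

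**The case against.** The best reply is that SAP 5.4.1 only lists endpoints. Its lead-in already carries the two time points, so the bullet may repeat them by habit. The adverse-event analysis that will actually be run is in 5.6.2, with a stated window, statistic and scope. No sentence excludes events after Week 32, no hypothesis test on adverse events is specified, and no data are lost.

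Much of this stands. A reader might infer that late adverse events disappear from the safety analysis. They do not: 5.6.2 keeps every reported TEAE. A reader might also take the share of follow-up time as the share by which safety is understated. That does not follow either: the SAP's statistic is the percentage with at least one event, which falls by less than proportionally. If the rate were instead events per person-time, a constant rate would give no bias at all. The Week 16 figure is no separate loss, because the same bullet also asks for Week 32.

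The absence of a safety objective from the SAP 1.1 table is not relied on here, since that table is visibly broken in the available copy.

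What the reply does not remove is the conflict. The time points are written into the bullet itself, under a heading for key confirmatory endpoints, and neither the protocol, 5.6.2 nor Appendix 2 supports them. If the phrase is carried over from the lead-in, it should go. If it is meant, it needs a definition.

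**Conclusion.** The point holds as a conflict over the time frame of a named secondary endpoint. The SAP text for that endpoint is wrong as written, but the SAP's safety analysis as a whole is not deficient on this account. Read literally, the endpoint stops 56 of 281 days early for a full course with 12-week follow-up. For participants stopped by the termination it stops 4 to 8 weeks before a 12-week post-dose period ends, if Week 32 is taken as the Final Efficacy Visit. The gap is smaller for those whose Final Safety Visit is an earlier first commercial dose.

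The documents give neither the mix of last-dose weeks nor the number who switched, so no overall figure can be stated. The reduction of about 5 to 8 percentage points applies to a full course only, and rests on the constant hazard and the 30% to 70% range assumed above.

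**What to change.** In SAP 5.4.1, delete the two time points from the adverse-event bullet. State that the endpoint is the number and percentage of guselkumab-treated participants with at least one TEAE over the full 5.6.2 window. Use the 5.6.2 start (adenosine or guselkumab) as well as its end, so that the endpoint agrees with the TEAE tables. Starting the endpoint at the first guselkumab dose without comment would create a new mismatch; if only those events are meant, say so and show them as a subset.

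Present any Week 16 or Week 32 figure only as a supplementary cumulative cut, with a statement of whether Week 32 means day 225 or the Final Efficacy Visit. Record any intended departure from the protocol endpoint in Appendix 2.

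The cost is SAP wording only. No new data are needed, and the 5.6.2 tables already use the longer window.

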5.4.1.1. Definition of Endpoint(s)

Refer to Section 5.3.1 for Definition of CFR Endpoint

The secondary endpoint for the study is the change from baseline in CFR at Week 16 or GLS/cf-PWV at Week 16 and Week 32 are based on FAS.

5.4.1.1.1. Global Longitudinal Strain (GLS) for Left Ventricular Function

In the G-CARE study, speckle tracking echocardiography (STE) will be employed for the detection of left-ventricular (LV) myocardial strain. Two-dimensional STE is based on the temporal and spatial tracking of naturally occurring intramyocardial reflectors of ultrasound (speckles) within the 2D echocardiographic images of the LV walls, and measures LV regional and global deformations as a marker of contractility and elasticity. The GLS and global longitudinal strain rate will be calculated at systole and diastole. The ratio of the arterial stiffness measured with cfPWV (described below) and the myocardial performance represented by GLS will be calculated as an index reflecting the arterial-ventricular interaction. In addition, the estimated LV peak twisting and untwisting at the time of mitral valve opening will be measured, and the percentage difference between LV twist and untwisting at the mitral valve opening will be calculated.

The strain-pressure curves recorded from the GLS measurement may be used to calculate the myocardial work index at selected sites.

5.4.1.1.2. Carotid-femoral Pulse Wave Velocity (cf-PWV)

The measurement of cfPWV is accepted as the most simple, non-invasive, robust, and reproducible method to determine arterial stiffness.28 Carotid-femoral (cf) PWV is a direct measurement, and it corresponds to the widely accepted propagative model of the arterial system. Measured along the aortic and aorto-iliac pathway, it is the most clinically relevant since the aorta and its first branches are what the left ventricle 'sees' and are thus responsible for most of the pathophysiological effects of arterial stiffness. cfPWV is usually measured using the foot-to-foot velocity method from various waveforms. These are obtained transcutaneously at the right common carotid artery and the right femoral artery (ie, 'carotid-femoral' PWV), and the time delay (\Delta to transit time) measured between the feet of the 2 waveforms. A variety of different waveforms can be used including pressure, distension, and Doppler. The distance (D) covered by the waves is usually assimilated to the surface distance between the 2 recording sites. cfPWV is calculated as cfPWV=D (meters)/\Delta t (seconds). Average of triplicate cfPWV measurements will be derived and used for the analysis at each of the treatment time point.

Data Handling Rules for Efficacy Analyses

The secondary efficacy analyses (eg, over time summaries), after the treatment failures are applied, no imputation will be performed for missing data (eg, lost to follow-up, missed study visit) and the values will remain as missing and as observed data will be used for the analysis.

5.4.1.2 Estimand

Secondary Trial Objective: To evaluate the effect of guselkumab on CFR/GLS/cf-PWV measured by transthoracic doppler-echocardiography, in participants with moderate-to-severe psoriasis and intermediate cardiovascular risk. Intermediate cardiovascular risk is defined by CFR ≥ 2 and ≤ 3.5 at Screening Visit S2.

Estimand Scientific Question of Interest: What level of change from baseline of CFR/GLS/cf-PWV considered to have benefited from guselkumab for the pre-specified duration (16 weeks).

Study intervention:

• Guselkumab (100 mg SC [Subcutaneous] injections at Week 0, 4, 12, 20 and 28)

Population: Participants with moderate to severe plaque psoriasis (with or without PsA) for at least 6 months prior to study entry. The target population consists of men or women aged 18 years and above with moderate to severe plaque psoriasis of at least 6 months' duration, defined as PASI \geq 12, and involved BSA \geq 10% at Screening Visit S1 and CFR with \geq 2 to \leq 3.5 at Screening Visit S2. Participants should not be with CFR of \leq 0 r \geq 3.5 at both Screening Visit S2 and Week 0.

Variable: Change from baseline in the CFR measurement at Week 16. The CFR measurement at Week 0, Baseline will be considered as baseline value. Similarly, for other secondary endpoints of GLS/cf-PWV at Week 16 and Week 32. Participants who had adequate secondary endpoint measurements will be assessed at Week 16 as per Table 2 and Final Efficacy Visit (Week 32) considering as observed for the analysis.

Secondary Estimand:

Summary measure (Population-level summary): LSmeans, together with the 95% CI and p-values based on the MMRM.

Intercurrent events and their corresponding strategies:

Intercurrent Events	Strategy for Addressing Intercurrent Events and Its Description
	Composite Strategy: A participant with this intercurrent event will be excluded from the analysis.

5.4.1.3 Analysis Methods

Main Estimator (Analysis) for the Primary Estimand

A MMRM will be used to determine the change from baseline in Cardiovascular measurement at Week 16 or Week 32 in the open label phase to compare the participant groups of nicotine users vs non-nicotine users, will be analyzed using a MMRM based on observed case data. The models will include baseline CFR/GLS/cf-PWV measurement at Week 0, Baseline before first administration of guselkumab as a covariate, and Nicotine use, BMI, presence, or absence of PsA, age, gender, and visit.

The estimates for the primary estimand of the treatment effect of guselkumab will be provided by the difference of change from baseline at Week 32 in the LSmeans. The 95% CI for the differences in LSmeans and p-values will be calculated based on the MMRM. The within-subject covariance between visits will be estimated via an unstructured variance-covariance matrix. In case of convergence problems, alternative variance-covariance structures will be tried in the following order, with the first structure that converges being used in the analysis: heterogeneous Toeplitz, standard Toeplitz, and AR(1) with separate subject random effect.

5.5. Tertiary/Exploratory Endpoint(s) Analysis:

As the study was prematurely terminated all exploratory endpoints will be presented by listing only with change from baseline where applicable.

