## **Rationale for Study Duration**

Previous studies investigating the effects of adalimumab and phototherapy, and secukinumab (VIP-S), on psoriasis and surrogate cardiovascular risk markers by evaluating the primary endpoint after 12 weeks of intervention, failed to demonstrate a significant change in vascular inflammation. A study using flow mediated dilatation of the brachial artery also failed to demonstrate a significant improvement at 12 weeks versus placebo (primary endpoint) but clearly

showed a dose and time dependent effect with a statistically significant effect at 52 weeks of secukinumab treatment. Ustekinumab, an IL-12/23 blocker has demonstrated a significant improvement of vascular inflammation after 12 weeks. In all studies the effect on skin improvement was in line with previous results in clinical trials.

These observations hint towards the assumption that cardiovascular inflammation of peripheral arteries assessed by surrogate markers improve slower than the skin parameters (eg, PASI, IGA). Therefore, the rationale for G-CARE is to assess the primary endpoint at Week 32 and assess a secondary endpoint at Week 16 for a detailed investigation of the timeline of effects of guselkumab on the coronary system. Further, these results will be correlated with the timeline of skin improvement. These results will help to better understand the effect of long-term treatment and the effects on cardiovascular endpoints like myocardial infarction, stroke, and cardiovascular death.

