5. STATISTICAL ANALYSES

5.1. General Considerations

Descriptive statistics (eg, mean, median, standard deviation (SD), minimum, and maximum) will be used to summarize continuous variables. Counts and percentages will be used to summarize categorical variables. Graphic data displays may also be used to summarize the data. In addition, graphical data displays (eg, line plots) and participant listings may also be used to summarize the data.

The summarized data will be presented by Nicotine-user, non-Nicotine user and total group.

Baseline Value: For all endpoints the last non-missing measurement prior to or on the day of the first administration of the study treatment (guselkumab) will be the Baseline value in the study (i.e., at 'Week 0, Baseline' analysis visit, following assignment of the actual visits using visit windows, as indicated in Table 2).

Level of Significance: In general, all tests will be performed at a 2-sided significance level of 0.05, unless otherwise specified. All interval estimations will be reported using 2-sided 95%CI. Nominal p-values will be presented.

Change from Baseline:

For the continuous variables pertaining to the cardiology outcomes, skin related outcomes, or paper PRO outcomes the determination of change from baseline will be determined only when both, baseline and the measurement for the particular visit is available.

Change from Baseline at visit x = Measurement from the visit x - Baseline value of the parmeter

The number of patients with missing change from baseline values will be also presented in the statistical outputs.

For continuous or ordinal efficacy endpoints, a Mixed-effect Model for Repeated Measures (MMRM) will be used. Covariates such as Nicotine use, body mass index (BMI), presence, or absence of PsA, age, gender, and visit will be incorporated into these models.

For binary efficacy endpoints, 95% confidence interval [CI] for binomial proportions will be provided using exact methods, such as Clopper-Pearson or Chan-Zhang.

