5.3.3. Analysis Methods

5.3.3.1. Main Estimator (Analysis) for the Primary Estimand

A MMRM will be used to determine the change from baseline in Cardiovascular measurement at Week 32 or Week 16 in the open label phase to compare the participant groups of nicotine users vs non-nicotine users, will be analyzed using a MMRM based on observed case data. The models will include baseline CFR measurement at Week 0, Baseline before first administration of guselkumab as a covariate, and Nicotine use, BMI, presence or absence of PsA, age, gender, and visit.

The estimates for the primary estimand of the treatment effect of guselkumab will be provided by the difference of change from baseline at Week 32 in the LSmeans. The 95% CI for the differences in LSmeans and p-values will be calculated based on the MMRM. The within-subject covariance between visits will be estimated via an unstructured variance-covariance matrix. In case of convergence problems, alternative variance-covariance structures will be tried in the following order, with the first structure that converges being used in the analysis: heterogeneous Toeplitz, standard Toeplitz, and autoregressive order 1 (AR[1]) with separate subject random effect.

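### The MMRM lists nicotine use and visit without their interaction, so as written it forces the same user/non-user difference at Weeks 16 and 32, although the secondary endpoints are defined by group and by week.

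*SAP*

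**What the plan says.** SAP 5.4.1 lists among the secondary endpoints "Change from baseline in CFR at Week 16 and Week 32 among nicotine users and non-users", and words GLS and cfPWV in the same way. Each outcome therefore has four target means: two groups at two weeks.

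SAP 5.4.1.2 makes the MMRM LSmeans, with confidence intervals and p-values, the summary measure. Section 5.4.1.3 says that the model is used "to compare the participant groups of nicotine users vs non-nicotine users" and takes its estimate from the "difference of change from baseline at Week 32 in the LSmeans". Both visits enter one fit, since visit is a model term and the covariance between visits is unstructured.

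The terms appear in three places:
- SAP 5.3.3.1 (primary): the baseline value "as a covariate, and Nicotine use, BMI, presence or absence of PsA, age, gender, and visit".
- SAP 5.4.1.3 (secondary): the baseline value, then "Nicotine use, BMI, presence, or absence of PsA, age, gender, and visit".
- SAP 5.1 (general): "Covariates such as Nicotine use, body mass index (BMI), presence, or absence of PsA, age, gender, and visit will be incorporated into these models".

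None of them names a nicotine-by-visit or a baseline-by-visit product.

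**The concern.** A model with nicotine use and visit as separate terms assumes that the two groups follow parallel profiles. The user minus non-user difference at Week 16 and the one at Week 32 are then the same number with the same p-value. If the groups respond at different speeds, each group-by-week LSmean is pulled toward what the other visit shows, and a contrast labelled Week 32 is a mixture of both visits.

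Timing is part of the study's question. Protocol 4.2 gives the reason for the earlier measurement: to "assess a secondary endpoint at Week 16 for a detailed investigation of the timeline of effects of guselkumab on the coronary system". An additive model shows that timeline for the cohort as a whole, but assumes away any difference in it between users and non-users.

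**Working it through.** The plan gives no figure for the user/non-user contrast, so there is none to reproduce. The check is an illustration of what the listed terms do.

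**Inputs from the SAP.** 20 users and 30 non-users (Figure 1 in 1.2); SD 0.8 (section 3).

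**Assumed.** The same SD at both visits; within-person correlation 0.5; complete data; other covariates left out. True mean changes: users 0.10 at Week 16 and 0.10 at Week 32; non-users 0.10 and 0.40. The true difference (users minus non-users) is 0 at Week 16 and -0.30 at Week 32.

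**Parameter count.** The additive model is intercept + nicotine + visit: three parameters for four means. The group difference is the nicotine coefficient at either visit.

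**Difference under the additive model.** With equal variances and complete data, generalised least squares weights the visits equally: 0.5 x 0 + 0.5 x (-0.30) = -0.15, reported at both weeks. This holds for any common correlation.

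**Whole-cohort means at observed weights (0.4 and 0.6).**
- Week 16: 0.4 x 0.10 + 0.6 x 0.10 = 0.10.
- Week 32: 0.4 x 0.10 + 0.6 x 0.40 = 0.28.

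Both are the same with and without the interaction.

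**Group-by-week LSmeans under the additive model.** Users are the cohort mean + 0.6 x (-0.15); non-users are the cohort mean - 0.4 x (-0.15).

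| | True | Additive model | With nicotine x visit |
|---|---|---|---|
| Users, Week 16 | 0.10 | 0.01 | 0.10 |
| Users, Week 32 | 0.10 | 0.19 | 0.10 |
| Non-users, Week 16 | 0.10 | 0.16 | 0.10 |
| Non-users, Week 32 | 0.40 | 0.34 | 0.40 |
| Difference, Week 16 | 0 | -0.15 | 0 |
| Difference, Week 32 | -0.30 | -0.15 | -0.30 |

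**Standard error of the difference.**
- Additive: variance of a person's two-visit mean = 0.64 x (1 + 0.5)/2 = 0.48; 0.48 x (1/20 + 1/30) = 0.04; SE 0.200.
- With interaction: 0.64 x (1/20 + 1/30) = 0.0533; SE 0.231.

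**Sensitivity to the covariance.** With variances 0.40 and 0.64 and covariance 0.30, the Week 32 weight is (0.40 - 0.30)/[(0.64 - 0.30) + (0.40 - 0.30)] = 0.10/0.44 = 0.227, so the common difference is 0.227 x (-0.30) = -0.068.

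**Sensitivity to missing data** (equal variances, correlation 0.3 to 0.7, half of each group missing at one visit).
- Half of Week 32 missing: common difference -0.08 to -0.09; users at Week 32 about 0.23.
- Half of Week 16 missing: common difference -0.21 to -0.22; users at Week 32 about 0.15.

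The pooled value moves toward the true difference at whichever visit has more data.

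**The case against.** The strongest reply is that the SAP never excludes an interaction. Section 5.1 introduces its list with an open phrase, and section 1 leaves programming instructions to a separate specification that is not available here. That is fair as far as it goes: the gap is something not specified, not something forbidden. But 5.3.3.1 and 5.4.1.3 state what the models will include without that qualifier, and a programmer following them would fit the additive model.

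Second, section 5.1 also presents summarised data by nicotine group, and such summaries need no model. This stands, but 5.4.1.2 names the MMRM LSmeans as the summary measure, so the descriptive tables do not replace them.

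Third, the divergence in the illustration is chosen. No document predicts that users and non-users separate over time, and Protocol 4.2 speaks of the overall time course. If the profiles are parallel, the additive model is unbiased and more precise. This stands as a limit on the size, not on the constraint.

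Two stronger readings are tempting and should be set aside:
- A reader might infer that the week-specific endpoints cannot be estimated at all. They can: the model returns an LSmean for each group at each week, held to parallel profiles, and the whole-cohort means by week are identified through the visit term.
- A reader might infer that early termination made Week 32 the sparser visit, so that its subgroup result is mostly a Week 16 result. The documents do not say so. SAP 1.2 keeps Final Efficacy Visits after termination and advises against some per-protocol visits that would add a second cardiovascular assessment within a short time. Table 2 (footnote c) and Appendix 2 analyse the Final Efficacy Visit as Week 32. Week 16 may equally be the sparser one.

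**Conclusion.** The point holds as a specification gap. With the terms listed in SAP 5.3.3.1 and 5.4.1.3, the user minus non-user difference in CFR, GLS and cfPWV change is constrained to be equal at Weeks 16 and 32, while the endpoints are defined by group and week. Any such contrast labelled Week 32, and the group-by-week LSmeans, then pool both visits.

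Under the assumed truth above, the error in the difference is 0.15 at each week, and the group means are off by 0.09 (users) and 0.06 (non-users). These sizes rest on the assumed divergence, the planned 20/30 split, equal variances and complete data. With missing data, size and direction depend on which visit is sparser, which the documents do not state. Whole-cohort means by week at observed weights are not affected in these scenarios. The SAP presents p-values as nominal, so the consequence is misleading subgroup estimates rather than a failed confirmatory test. The change is worth making because it is cheap.

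**What to change.** In SAP 5.3.3.1 and 5.4.1.3, add nicotine use x visit to the listed terms. State that LSmeans and contrasts are taken by visit, and report them for users, non-users and overall. Baseline value x visit is an optional refinement if the data allow; no bias from leaving it out has been shown, and in a small sample the nicotine term should come first.

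The cost is a line of wording, one extra parameter per model and a wider interval for the visit-specific group difference. At the planned size, with correlation 0.5 and complete data, the standard error goes from 0.200 to 0.231, about 15% wider (0.231/0.200 = 1.155). With half of Week 32 missing it goes from 0.214 to 0.306. The final sample is smaller than planned, so the actual intervals will be wider still. That width is the honest precision for a Week 32 contrast; the narrower interval is obtained by assuming that the two weeks agree.
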